5.2.2 Exclusion Criteria

- 1. Subject is considered by the Investigator, for any reason, to be an unsuitable candidate for continuing therapy in the Study M10-870.
- 2. Female subjects who are pregnant or currently breastfeeding or considering becoming pregnant during the study.
- 3. Subject with Crohn's disease (CD) or indeterminate colitis (IC).

[figure not shown]

- 4. History of clinically significant drug or alcohol abuse in the last 12 months.
- 5. History of demyelinating disease (including myelitis) or neurologic symptoms suggestive of demyelinating disease.
- 6. History of chronic or active hepatitis B infection, human immunodeficiency virus (HIV) infection, any immunodeficiency syndrome, or active TB (regardless of receiving treatment), or active viral infection that, based on the investigator's clinical assessment, makes the subject an unsuitable candidate for the study.
- 7. History of moderate to severe congestive heart failure (NYHA class III or IV), recent cerebrovascular accident and any other condition which would put the subject at risk by participation in the study.
- 8. History of malignancy (including lymphoma and leukemia) other than a successfully treated non-metastatic cutaneous squamous cell or basal cell carcinoma or localized carcinoma in situ of the cervix.
- 9. Subject who is planning surgical bowel resection at any time point while enrolled in the study.
- 10. Known hypersensitivity to adalimumab or its excipients.
- 11. Current diagnosis of fulminant colitis and/or toxic megacolon.

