6.3 Toxicity Management

Subjects who develop a new infection while undergoing treatment with adalimumab should be monitored closely. Administration of study injections should be interrupted if a subject develops an infection requiring IV anti-infective treatment or if an infection meets the definition of "serious" (refer to Section 6.1.3 for definitions). Study medication may be restarted once the physician determines that the infection has been successfully treated. Otherwise prohibited concomitant medications may be given if medically necessary. Prior to use, every attempt should be made to contact the AbbVie Study Physician for direction on re-introduction of adalimumab therapy after prohibited medication administration.

If the subject must undergo elective surgery, the study injections must be interrupted 2 weeks prior to the surgery. If the subject must undergo emergency surgery, the study injections must be interrupted at the time of the surgery. The injectable study medication can recommence at least 2 weeks after surgery once the physician has examined the surgical site and determined that it has healed and there is no sign of infection.

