8.1.4 Efficacy Analysis

Summary statistics will be provided for each visit, based on observed data and non-responder imputation (NRI) for missing categorical data. An additional summary will be provided for the last visit, using the last observation carried forward (LOCF). That is, the subject's last non-missing, post-Baseline value (i.e., post-Week 52 Study M11-290 value) will be carried forward to the last visit. Details will be provided in the Statistical Analysis Plan (SAP).

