All time points and corresponding time windows are defined based on Rx days. The protocol specified visits and corresponding time windows are presented in the table below. Measures will only be displayed at the visits where they were planned to be measured. For example, Mayo score is collected at Weeks 0, 48, 96, 192 and 288/Premature Discontinuation (dependent on availability of optional endoscopy data at these timepoints).

Assigned Visit	Nominal Day	Time Window (Rx Day Range)
Week 0	1	≤ 1
Week 4	29	2 to 43
Week 8	57	44 to 71
Week 12	85	71 to 127
Week 24	169	128 to 211
Week 36	253	212 to 295
Week 48	337	296 to 379
Week 60	421	380 to 463
Week 72	505	464 to 547
Week 84	589	548 to 631
Week 96	673	632 to 715
Week 108	757	716 to 799
Week 120	841	800 to 925
Week 144	1009	926 to 1093
Week 168	1177	1094 to 1261
Week 192	1345	1262 to 1429
Week 216	1513	1430 to 1597
Week 240	1681	1598 to 1765
Week 264	1849	1766 to 1933
Week 288	2017	1934 to 2101

If more than one assessment is included in a time window the assessment closest to the nominal day should be used. If there were more than one observation with equal distance to the nominal day the latest one will be used in analyses. For any given variable, if more

than one measurement exists for a subject on the same day, the average of the measurements will be considered to be that subject's measurement for that day.

Missing Data Handling

In general, missing Baseline and safety data will not be imputed.

Baseline Value is Missing:

Subjects will be excluded from analysis of change from Baseline if Baseline evaluation is missing.

Missing Efficacy and Outcome Evaluations:

The following methods will be used for imputing missing values to perform the efficacy analyses.

[figure not shown]
For interim analyses, missing values will only be imputed up to the timepoint a patient could have potentially reached at the data cutoff for analyses.

Observed Cases (OC): missing values will not be used for the observed case analysis.

Last Observation Carried Forward (LOCF): For categorical and continuous efficacy variables the following rules will be used for LOCF approach:

- Baseline and pre-baseline values will not be used to impute the missing post-baseline values, and
- Missing values after baseline will be imputed using the last non-missing values after baseline and prior to the missing value.

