2. PUCAI

Pediatric Ulcerative Colitis Activity Index (PUCAI) is calculated as the sum of six subscores [each being a 2 day average, see above] of PUCAI (abdominal pain [no pain = 0, pain can be ignored = 5, pain cannot be ignored = 10], rectal bleeding [none = 0, small amount with < 50% of stools = 10, small amount with most stools = 20, large amount with > 50% of stool content = 30], stool consistency of most stools [formed = 0, partially formed = 5, completely unformed = 10], number of stools per 24 hours [0 to 2 = 0, 3 to 5 = 5, 6 to 8 = 10, > 8 = 15], nocturnal stools [no = 0, yes = 10], activity level [no limitation = 0, occasionally limited = 5, severe restriction = 10]) with maximum total score 85. Higher scores represent more severe disease.

- PUCAI remission is defined as PUCAI < 10.
- PUCAI response is defined as a decrease in PUCAI ≥ 20 points from Study M11-290-Baseline.

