10.1 General Considerations

No confirmatory testing for efficacy endpoints will be performed in this open-label study.

[figure not shown]
Endpoints that are of the binary type will be analyzed as proportions including 95% CIs. Endpoints that are of the continuous type will be analyzed as changes from baseline, and reported including 95% CIs. OC and LOCF (see Section 6.0) will be used, unless otherwise noted.

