10.2 Efficacy Analysis

The efficacy endpoints are:

- The proportion of subjects who achieve clinical remission as measured by PMS (defined as a PMS ≤ 2 and no individual subscore ≥ 1) over time;
- The proportion of subjects who achieve clinical response as measured by PMS (defined as a decrease in PMS ≥ 2 points and ≥ 30% from Study M11-290-Baseline) over time;
- The proportion of subjects who achieve PUCAI remission (defined as < 10) over time;
- The proportion of subjects who achieve PUCAI response (defined as a decrease in PUCAI ≥ 20 points from Study M11-290-Baseline).
- Change from Baseline in total IMPACT III Quality of Life score and subscores over time for subjects at least 9 years old at Baseline;
- Change from Baseline in WPAI scores over time;
- Change from Baseline in "z" scores for height over time;
- Change from Baseline in BMI over time;
- Change from Baseline in "z" scores for weight-for-age over time;
- Change from Baseline in albumin and total protein over time;
- Change from Baseline in hemoglobin, hematocrit, red blood cell count over time;
- Change from Baseline in hs-CRP levels over time;
- Proportion of subjects at appropriate Tanner stage (see Section 6.0) over time;
- Proportion of subjects in Mayo score clinical response over time (for subjects with available Mayo score);
- Proportion of subjects in Mayo score clinical remission over time (for subjects with available Mayo score);
- Proportion of subjects who achieve mucosal healing over time as measured by Mayo endoscopy subscore (defined as ≤ 1, for subjects with available Mayo score)
- Proportion of subjects in 9 point Mayo score (without PGA) clinical remission over time (for subjects with available Mayo score);

• Proportion of subjects in 6 point Mayo score (without PGA and endoscopy subscore) clinical remission over time (for subjects with available Mayo score).

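### The SAP sets no outcome after colectomy, so a child who has one can still be counted as a responder and, in some cases, as in remission

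*SAP*

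**What the plan says.** **Endpoints.** SAP 10.2 lists "The proportion of subjects who achieve PUCAI remission (defined as < 10) over time". For response, SAP 6.0 (Score Definitions) states: "PUCAI response is defined as a decrease in PUCAI ≥ 20 points from Study M11-290-Baseline". PMS response is "defined as a decrease in PMS ≥ 2 points and ≥ 30% from Study M11-290-Baseline". None of these, nor the Mayo-based definitions in SAP 6.0 Table 2, carries a condition about surgery.

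**Surgery.** Neither document uses the word colectomy. Bowel resection appears only as an entry exclusion (Protocol 5.2.2): "Subject who is planning surgical bowel resection at any time point while enrolled in the study". For surgery during the study, Protocol 6.3 interrupts dosing and then says: "The injectable study medication can recommence at least 2 weeks after surgery once the physician has examined the surgical site". Surgery is not named among the withdrawal criteria in Protocol 5.4.1.

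**Analysis rules.** The Full Analysis Set (SAP 5.1) keeps every treated subject. Visit windows (SAP 6.0) take the assessment nearest the nominal day. SAP 10.1 says "OC and LOCF (see Section 6.0) will be used, unless otherwise noted", and the LOCF rule is: "Missing values after baseline will be imputed using the last non-missing values after baseline and prior to the missing value". Protocol 8.1.4 describes summaries "based on observed data and non-responder imputation (NRI) for missing categorical data", but NRI is not among the SAP's methods. SAP 10.4 leaves sensitivity analyses open and specifies none.

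**The concern.** Colectomy in a child with UC means that medical treatment did not keep the disease under control or could not continue. Once the colon is out, bleeding and stool items no longer measure what they measured at the parent-study baseline. A low score then reflects the operation, not adalimumab. Scored by thresholds alone, such a subject can enter the numerator of the response or remission proportion.

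The stated objective includes maintenance of clinical response, so the error runs in the favourable direction on something the study sets out to describe. No hypothesis is tested, so type I error and power are not affected. What is affected is the reported proportions and their 95% confidence intervals.

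**Working it through.** The plan states no figure to reproduce here. The check follows the rules through, then does the score arithmetic. The clinical premise, which the documents do not state, is that bleeding from the removed colon stops.

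**1. Can a post-operative score enter the analysis?** Yes, if the subject stays on study. Dosing may recommence (Protocol 6.3), the subject remains in the Full Analysis Set, the windows accept the score, and no endpoint definition excludes it. The final evaluation (SAP 6.0) is the last non-missing value after first dose and is not cut at surgery.

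**2. Response from the bleeding item alone, all else unchanged from Study M11-290 Baseline.**
- PMS, bleeding subscore 3 to 0: the fall is 3 points, which meets the 2-point criterion. As a share of baseline PMS it is smallest at PMS 9, where 3/9 = 33.3%, above 30%. Response is met at every possible baseline PMS (3 to 9).
- PMS, bleeding subscore 2 to 0: 2/6 = 33.3% passes and 2/7 = 28.6% fails. Response is met at a baseline PMS up to 6.
- PMS, bleeding subscore 1 to 0: the fall is 1 point, so response is not met.
- PUCAI, bleeding item 30 or 20 to 0: the fall is at least 20, so response is met if the other items total no more than at baseline. From 10 to 0 it is not met on this item alone.

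**3. Remission.**
- PUCAI: with bleeding at 0, the other five items give 3 × 3 × 4 × 2 × 3 = 216 combinations (Protocol Appendix C). Five of them total below 10: all items zero, or exactly one of pain, consistency, stool number or activity at 5. The combinations are not equally likely, so 5/216 is not a probability; it shows only that remission is reachable. Completely unformed stool scores 10 and fails by itself.
- PMS: SAP Table 2 requires a total of at most 2 and every subscore below 1, so the physician's global assessment (PGA) must be 0. The Protocol synopsis sets the subscore cut-off at above 1, under which a PGA of 1 would not block remission by itself.
- Anti-diarrheal days score 15 for PUCAI stool number (Protocol 5.3.1.1) and 3 for Mayo stool frequency (Appendix D). Used on all scored days, such medication rules out both remissions.

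**4. If the subject leaves.** For elective surgery, injections stop 2 weeks beforehand (Protocol 6.3), and the Termination Visit is due within 2 weeks of the last dose (Protocol 5.4.1). On that schedule the last value is pre-operative. After emergency surgery the visit can fall after the operation. LOCF carries forward whichever value is last. A pre-operative value can itself be a response: baseline PMS 6 and last PMS 4 is a fall of 2 points, 2/6 = 33.3%.

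**5. Size.** Shift = k/n for k misclassified subjects, with N = 55 outside Japan (SAP 4.3).
- k = 1, 3, 5 (assumed) at N = 55: 1.8, 5.5 and 9.1 percentage points.
- k = 1 at assumed late-visit OC counts of 25 and 15: 1/25 = 4.0 and 1/15 = 6.7 points.
- Illustration with assumed counts and exact (Clopper-Pearson) intervals: 33/55 = 60.0% (45.9 to 73.0) becomes 30/55 = 54.5% (40.6 to 68.0) if three of the 33 had a colectomy.

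**The case against.** The strongest reply is that the problem will rarely arise. Protocol 5.4.1 withdraws subjects for clinically significant adverse events or when the investigator judges it in their interest, and Protocol 5.1 discontinues those with persistently uncontrolled disease on the top dose. Many subjects who need a colectomy would leave, often with a pre-operative last value recorded during active disease. Those who stay face the blocks to remission shown above, and stools that cannot be counted may leave the Mayo subscores missing. The study is descriptive and small enough for such cases to be recognised individually.

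Most of this stands, and it limits what can be claimed. A reader might infer any of the following, and the documents do not support them:
- *Every colectomised child will be scored in remission.* Remission is reachable but easily blocked; response is the likelier error.
- *Such children stay on adalimumab.* Protocol 6.3 is a general surgery provision that permits restarting. It does not show that they remain.
- *LOCF always carries a post-operative score.* Visit timing often makes the last value pre-operative.
- *Six-point remission is inflated in the same way.* SAP 10.2 limits it to subjects with an available Mayo score, which depends on endoscopy.
- *Surgery goes unreported.* An operation with hospital admission is an SAE (Protocol 6.1.3) and appears in the SAE tables and listings (SAP 11.2).

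What does not stand is that existing rules close the gap. The discontinuation rules assign no efficacy outcome. Restoring NRI would treat missing values as failures but would leave a favourable observed score untouched.

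**Conclusion.** The point holds in limited form. Under the written rules, a subject who has a colectomy and stays on study can be counted under OC as a PMS or PUCAI responder and, in some cases, as in remission. One who leaves can be carried forward as a responder. No endpoint definition, analysis set, imputation rule or named withdrawal criterion prevents either.

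Each misclassified subject is worth 1.8 points at N = 55, or 4.0 points at an assumed n = 25. The total cannot be projected, because the documents give no colectomy rate; the counts of 1, 3 and 5 are illustrations. The conclusion rests on the premise that colonic bleeding stops and on at least one such operation occurring. It is a cheap improvement to a descriptive analysis and not a flaw that invalidates it.

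**What to change.** Add one rule to SAP 6.0 and refer to it in SAP 10.2. From the date of colectomy, bowel resection for UC or stoma:
- Count PMS and PUCAI remission and response as not achieved at all later visits, under both OC and LOCF. For an interim analysis, stop at the last visit the subject could have reached by data cut-off, as SAP 6.0 already does for imputation.
- Do the same for the Mayo, 9-point and 6-point endpoints and mucosal healing wherever the subject is in the denominator.
- Do not carry a success forward past that date, whether it was recorded before or after surgery.

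Add one table row with the number of subjects with colectomy and the rate per 100 patient-years. Colectomy is not an adverse event of special interest in SAP 11.2, and the tables by organ class and preferred term do not isolate it.

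This is a scoring rule. It changes no treatment, visit, eligibility or withdrawal provision. The cost is one SAP paragraph, one table row and identification of the operation dates from safety records. If the database has no separate procedure field, a manual review of about 55 subjects would do. The downside is that reported rates can only become slightly less favourable.

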4. WPAI

The WPAI was developed to measure the effect of disease on productivity at work and its impact on daily activities. The questions ask about the impact of disease to the patient's caregiver within the past 7 days. Six questions asked on this questionnaire can be described briefly as follows:

Questions:

- Q1. Currently employed (working for pay)? (Yes/No)
- Q2. Hours missed from work due to PROBLEM.
- Q3. Hours missed due to other reasons.
- Q4. Hours actually worked.
- Q5. Degree PROBLEM affected productivity while working.
- Q6. Degree PROBLEM affected regular activities other than job.

WPAI scores are expressed as *percent impairment* based on the above questions. The four main impairment measures or scores are derived as follows:

Scores:

S1. *Absenteeism*: Percent work time missed due to PROBLEM:

$$100 \times \left[\frac{Q2}{O2 + O4} \right]$$

S2. **Presenteeism**: Percent impairment while working due to PROBLEM: $100 \times \left[\frac{Q5}{10} \right]$

S3. Percent *overall work impairment* due to PROBLEM:

$$100 \times \left[\frac{Q2}{Q2 + Q4} + \left\{ 1 - \frac{Q2}{Q2 + Q4} \right\} \times \frac{Q5}{10} \right]$$

S4. Percent *activity impairment* due to PROBLEM: $100 \times \left[\frac{Q6}{10} \right]$

5. Other

Body Mass Index (BMI, in kg/m²) will be obtained as:

 $BMI = weight (kg)/(height [m] \times height [m])$

"z" score for height velocity will be obtained as: (Observed height velocity [cm/yr] – mean height velocity for age and sex [cm/yr]/[SD of the mean]). NOTE: The mean and Standard Deviation (SD) will come from published table values: The CDC Growth Charts webpage of the Center for Disease Control and Prevention with derivation details on the "z" score:

[figure not shown]
http://www.cdc.gov/growthcharts/percentile_data_files.htm, STATAGE.xls ('stature-for-age-chart,' for height) to be used.

Inappropriate Tanner stage will be defined depending on age and sex as follows: $girls \ge 14$ years/boys ≥ 15 of age with a Tanner stage of 1; $girls \ge 16$ years/boys ≥ 18 of age with a Tanner stage < 4; $girls \ge 19$ years/boys ≥ 19 of age with a Tanner stage of < 5.1.

7.0 Demographics, Baseline Characteristics, Medical History, and Previous/Concomitant Medications

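### BMI change is analysed raw as an efficacy endpoint in growing children, while height and weight in the same list are z-scored, so expected growth enters the reported change and its 95% CI

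*SAP*

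**What the plan says.** SAP 10.2 includes three body-size measures among its efficacy endpoints. Two are standardised: z "scores for height over time" and z "scores for weight-for-age over time". The third, listed between them, is "Change from Baseline in BMI over time", with no standardisation.

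SAP 6.0, Score Definitions, item 5 (Other), gives the derivations. "Body Mass Index (BMI, in kg/m²) will be obtained as" weight divided by height squared, and no z-score or percentile follows. The reference source is "The CDC Growth Charts webpage of the Center for Disease Control and Prevention", and the one file named is "STATAGE.xls ('stature-for-age-chart,' for height) to be used". No file is named for weight or for BMI.

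SAP 10.1 sets the analysis: "Endpoints that are of the continuous type will be analyzed as changes from baseline, and reported including 95% CIs". For missing values, "OC and LOCF (see Section 6.0) will be used, unless otherwise noted".

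Protocol 5.3.2 makes the same split. It names z-scores for height and weight but plain BMI, all as further measures of disease activity. SAP 11.4 also lists raw BMI with the vital signs.

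**The concern.** A raw change from Baseline in a child combines two things: the movement expected from being older, and any movement relative to children of the same age and sex. For height and weight the plan reports a quantity that takes out the first part. For BMI, which is computed from those same measurements, it does not, and it gives no reason for the difference.

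The study is open-label and single-arm, so no comparison group removes growth. An interval for raw BMI change that excludes zero cannot show whether children moved up relative to their peers or simply got older. The risk is that a descriptive efficacy result is misread.

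**Working it through.** **Inputs from the documents**
- Open-label maintenance of 288 weeks plus 70 days of follow-up, 298 weeks in all (Protocol 5.1).
- Last planned height and weight for BMI at Week 288 or premature discontinuation (Protocol 5.3.1.1, Anthropometric Evaluations).
- Population aged 4 to 17 years (Protocol 3.3.1).
- About 55 subjects expected outside Japan (SAP 4.3), the group this SAP covers.

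**Inputs assumed, because the documents give none**
- Normal BMI gain of 0.3 to 0.7 kg/m² per year.
- SD of BMI change of 2 to 4 kg/m².

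**Step 1: the horizon.** 288 + 70/7 = 298 weeks, which reproduces the plan's figure. The last BMI is at Week 288, so the relevant time is 288 × 7/365.25 = 5.52 years. A child aged 5 at Baseline would then be about 10.5, and one aged 13 about 18.5.

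**Step 2: growth contained in the raw change.** Expected change with no shift in centile = annual gain × years.

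| Visit | Years | At 0.3 per year | At 0.7 per year |
|---|---|---|---|
| Week 48 | 0.92 | +0.28 | +0.64 |
| Week 96 | 1.84 | +0.55 | +1.29 |
| Week 288 | 5.52 | +1.66 | +3.86 |

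For a BMI-for-age-and-sex z-score, the same child has an expected change of 0 at every visit.

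**Step 3: comparison with the planned interval.** The 95% CI half-width is t(0.975, N−1) × SD/√N.
- N = 55: 0.54, 0.81 and 1.08 kg/m² for SD 2, 3 and 4. Dividing by 5.52 years, an average reference gain above about 0.10, 0.15 or 0.20 kg/m² per year would by itself put the Week 288 interval above zero.
- N = 25, chosen to illustrate fewer observed cases late in the study: 0.83, 1.24 and 1.65 kg/m². The corresponding gains are 0.15, 0.22 and 0.30 per year.

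These thresholds refer to the average gain over all subjects analysed, each measured at Week 288. Subjects with little or no further growth lower that average.

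**Step 4: the effect of LOCF.** A subject who leaves at Week 48 has raw BMI fixed at that age. In the table that carries forward a growth component of +0.28 to +0.64, where a completer has +1.66 to +3.86. The pooled raw change at Week 288 therefore also depends on when subjects leave. For a child on a constant centile, the carried-forward z-score change is 0 whenever the child leaves.

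**Step 5: whether anything else in the plan covers this.**
- The age subgroups in SAP 10.5 (below 13, 13 and over) apply only to PMS remission and Mayo remission.
- SAP 10.4 allows sensitivity analyses but specifies none.
- Weight-for-age z does not adjust for height, and separate mean changes in height z and weight z do not give each subject's BMI relative to age and sex.

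**The case against.** The strongest reply is that little depends on this endpoint. It is one of 18 listed in SAP 10.2, and all are descriptive. SAP 10.1 rules out confirmatory testing, and the objective is safety, tolerability and maintenance of response. Height and weight z-scores are reported beside BMI and partly show whether weight outpaces height. The SAP also follows the protocol, which itself names plain BMI. All of this stands and sets the priority. It does not supply the missing standardisation.

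The size can also be challenged, with reason. The growth rate is assumed. Both documents allow for subjects who do not fit a straight 5.5-year projection:
- The bone-age rules in the protocol provide for height velocity of 0.
- Protocol 5.4.2 lets the study conclude about 12 weeks after approval (with the reimbursement application submitted) or a sponsor decision.
- SAP 8.0 counts a switch to adult care or to commercial drug as completion.

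A reader might infer that BMI must rise whatever the drug does, and that the rise will be presented as nutritional benefit. The documents support neither step. They contain no BMI growth data and do not say how a BMI change will be interpreted.

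A reader might also suppose that a suitable reference is already in use. SAP 6.0 names only the stature-for-age file. Its one written z formula is for height velocity, although it points to that stature-for-age table, so it cannot simply be reused for BMI.

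**Conclusion.** The point holds as a low-priority improvement. The planned BMI efficacy summary reports a change and 95% CI that include expected growth for age and sex. The height and weight endpoints in the same list are standardised, and no control arm removes the growth from BMI.

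The illustration of about +1.7 to +3.9 kg/m² at Week 288 applies to a still-growing child who completes, under an assumed gain of 0.3 to 0.7 kg/m² per year. It should not be read as a forecast of the cohort mean, which would be smaller where subjects have stopped growing or leave early.

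It may be tempting to conclude that a z-score would separate treatment effect from growth. It would not: it removes expected growth only. Steroid changes (permitted by Protocol 5.2.3.2), disease course and drop-out would remain mixed with any drug effect. No test, error rate or sample size is affected.

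**What to change.** - In SAP 10.2, add change from Baseline in BMI-for-age-and-sex z-score, and state that this is the BMI efficacy summary to be interpreted.
- Keep raw BMI as a descriptive line; it is already in SAP 11.4. Adding fits better than replacing, because the protocol names BMI among its efficacy measures.
- In SAP 6.0, name the BMI-for-age reference and write out the z-score derivation.
- In the same place, state a rule for subjects older than the reference's upper age limit. A subject aged 13 at Baseline would be about 18.5 at Week 288.

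The cost is one derived variable and the age rule. No new data are needed: sex, birth date, height and weight are already collected. Protocol 8.1 requires the SAP to be final before database lock, so the addition belongs before that point.
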